#### Study design

The MANCTRA-1 study (coMpliAnce with evideNce-based cliniCal guidelines in the managemenT of acute biliaRy pancreAtitis) is an international multicenter, retrospective cohort study to assess the outcomes of patients admitted to hospital with a diagnosis of biliary AP and the compliance of surgeons worldwide to the most up-to-dated international guidelines on biliary AP. The study compares data collected in 2019 (pre-pandemic period) with those of 2020 (Covid-19 pandemic period).

#### **Study population**

All consecutive adult patients admitted to the participating surgical departments with a clinical and radiological diagnosis of biliary AP (with and without concomitant cholecystitis) between 01/01/2019 and 31/12/2020. Patient data will be retrospectively analyzed and demographic characteristics, comorbidity status, clinical and radiological findings, treatment strategies, 30-day morbidity and mortality will be evaluated.

#### Inclusion criteria

Patients of both sexes,  $\geq 16$  years old, admitted to any of the participating surgical departments and/or

coMpliAnce with evideNce-based cliniCal guidelines in the managemenT of acute biliaRy pancreAtitis (MANCTRA-1). internal medicine or gastroenterology departments for biliary AP in 2019 and 2020.

#### **Exclusion criteria**

Patients with AP of etiology other than gallstones; Pregnant patients.

#### **Study periods**

The pre-pandemic period runs from 01/01/2019 to 31/12/2019. The Covid-19 pandemic period runs from 01/01/2020 to 31/12/2020. Data will be entered in the database from 01/03/2021 to 31/08/2021.

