#### **COVID-19 and management of AP**

In 2020, the spread of the virus Covid-19 had represented a pandemic, which also profoundly impacted the surgical community [24, 25]. The constant increase in the number of patients requiring treatment has represented a massive challenge for many involved countries' healthcare systems and could be their breaking point. In an emergency situation, resources must be concentrated and used rationally to handle the pandemic and continue handling the pre-existing diseases. In this context, most surgical departments were forced to re-schedule their activity, giving priority to urgent/emergent surgical cases and non-deferrable oncological cases. There are many ways the outbreak of the Covid-19 pandemic could have influenced daily clinical practice for patients with biliary AP, leading to a failure to adhere to the recommendations coming from the guidelines, especially those regarding the early and definitive treatment with cholecystectomy or ERCP and sphincterotomy. First of all, the recommendation to postpone all non-urgent endoscopic procedures during the peak of the pandemic. Second, the recommendation to conservatively treat inflammatory conditions such as acute cholecystitis and acute appendicitis wherever possible.

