#### Sample size

Studies on biliary AP found a mortality rate of approximately 10%. Patients with biliary AP tend to have a higher mortality than patients with alcoholic pancreatitis. However, this rate has been falling over the last 2 decades as improvements in supportive care have been initiated. In patients with severe disease (organ failure), who account for about 20% of presentations, mortality is approximately 30%. This rate has not decreased in the past 10 years.

We estimate that a minimum of 200 patients per group (2019 vs. 2020) would yield a power of 0.80 (1β) to establish whether changes in clinical care for patients with biliary AP during the Covid-19 pandemic has impacted on overall mortality using a one-sided significance a level of 0.05 (5%) with power sample size calculator (sealedenvelope.com).

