## Section 2 – Demographic Characteristics

- ! Year of hospital admission for acute biliary pancreatitis (2019 Vs. 2020)
- ! Patient age
- ! Sex (Female Vs. Male)
- ! Covid-19 status on admission (Negative/Positive/Untested)

- ! Previous episodes of biliary pancreatitis (Yes/No)
- ! Admitting speciality (HPB surgery/General Surgery/Internal Medicine/Gastroenterology)

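### The 2020 group counts as pandemic care from 1 January and only the year of admission is recorded, so any 2020 admissions that preceded a change in care cannot be separated or examined

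*Combined protocol and SAP*

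**What the plan says.** The Study periods section defines both groups by calendar year: "The pre-pandemic period runs from 01/01/2019 to 31/12/2019" and "The Covid-19 pandemic period runs from 01/01/2020 to 31/12/2020". The same boundary applies to every participating country. The primary outcomes (30-day mortality and morbidity) and two secondary outcomes (early definitive treatment and 30-day readmission) are all set out as 2019 against 2020.

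The only CRF item that places an admission in calendar time is in Section 2: "Year of hospital admission for acute biliary pancreatitis (2019 Vs. 2020". None of the 14 CRF sections holds a month or date of admission or discharge. The nearest other item, "Covid-19 status on admission (Negative/Positive/Untested", describes the patient's infection and not the calendar: a negative or untested patient could have been admitted in January or in November 2020.

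The background section on COVID-19 and management of AP gives two ways in which the pandemic could have changed care. The first is "the recommendation to postpone all non-urgent endoscopic procedures during the peak of the pandemic". The second, conservative treatment of inflammatory conditions, carries no time limit. The Statistical analysis section plans no analysis with a later start to the pandemic period.

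**The concern.** The Aim of the study section asks whether care during the pandemic led to more adverse outcomes through weaker compliance with guidelines. The protocol itself ties one of its two mechanisms to a peak, so exposure to changed care probably varied within 2020. The design nevertheless codes it as constant from 1 January, in every country.

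If some early-2020 patients were treated as they would have been in 2019, the 2020 group mixes exposed and unexposed patients. The year contrast then understates the effect of changed care in the months when care did change. A null result would be ambiguous between no pandemic effect and dilution, and the planned dataset could not tell the two apart.

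**Working it through.** **Inputs from the Sample size section.** 200 patients per group, power 0.80, one-sided significance level 0.05, and a background mortality of about 10%. No 2020 mortality rate is stated, and the 10% is not expressly named as the 2019 rate. Using it as the reference is my assumption.

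**Step 1: the difference that 200 per group can detect.** With pooled variance under the null,

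power = Φ[(p₂ − p₁ − 1.645·SE₀) / SE₁], where SE₀ = √[2·p̄(1 − p̄)/n], p̄ = (p₁ + p₂)/2 and SE₁ = √[(p₁(1 − p₁) + p₂(1 − p₂))/n].

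With p₁ = 0.10 and n = 200, solving for 80% power gives p₂ = 0.1869. Check: p̄ = 0.1435, SE₀ = 0.0351, SE₁ = 0.0348, and (0.0869 − 1.645 × 0.0351)/0.0348 = 0.84, so power is 80%. The illustrative contrast is therefore 10% vs 18.7%, a difference of 8.7 points. The 18.7% is solved back from the plan's figures and does not appear in the plan.

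**Step 2: dilution.** Suppose m months of 2020 were unaffected, admissions were even over the year, patients in those months died at the 2019 rate, and 18.7% applied in the remaining months. Then

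observed difference = 8.69 × (12 − m)/12 points.

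For m = 2 this is 8.69 × 10/12 = 7.2 points, a 2020 rate of 17.2%. With SE₀ = 0.0343 and SE₁ = 0.0341, (0.0724 − 1.645 × 0.0343)/0.0341 = 0.47, so power is 68%.

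**Step 3: dropping the same m months from both years.** The difference returns to 8.7 points with n = 200 × (12 − m)/12 per group. For m = 2, n = 167, SE₀ = 0.0384 and SE₁ = 0.0381, so (0.0869 − 1.645 × 0.0384)/0.0381 = 0.62 and power is 73%.

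| Unaffected months (assumed) | 2020 rate | Difference, points | Power, whole years, 200 per group | n per group for 80%, whole years | n per group, months dropped from both years | Power, months dropped |
|---|---|---|---|---|---|---|
| 0 | 18.7% | 8.7 | 80% | 200 | 200 | 80% |
| 1 | 18.0% | 8.0 | 74% | 234 | 183 | 77% |
| 2 | 17.2% | 7.2 | 68% | 277 | 167 | 73% |
| 3 | 16.5% | 6.5 | 61% | 334 | 150 | 69% |

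Under these assumptions the restricted comparison has more power in each row with unaffected months, despite fewer patients, and it estimates the undiluted difference. Recruiting more patients restores power but leaves the estimated difference at 8.0, 7.2 or 6.5 points.

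**The case against.** The calendar-year contrast is a defined comparison, used consistently in the objectives, outcomes, design and study periods. It balances season and needs no country-by-country judgement about when care changed. If the whole-year difference is what the sponsor wants, it is estimated without bias. That stands, and it is the reason to keep this comparison. It does not help the reader interpret a small difference, and using the same calendar months of 2019 preserves the seasonal balance.

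Three stronger readings are tempting, and the documents do not support them.

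- A reader might infer that the stated power of 0.80 is not reached. The Sample size section gives no 2020 rate, describes the groups as whole years, and offers 200 only as "a minimum" in substance: "We estimate that a minimum of 200 patients per group (2019 vs. 2020) would yield a power of 0.80". A target difference set for the whole year would already average over all months. The study also takes all consecutive patients at many centres, so the 234, 277 or 334 per group in the table may well be exceeded.
- A reader might take the dilution as established. The documents give no date, for any country, on which care changed. Both the existence and the number of unaffected months are assumptions.
- A reader might suppose that both mechanisms are confined to the peak. Only the postponement of endoscopy is.

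Two further limits apply. The bar on early-2020 analyses holds for the CRF as written; the study is retrospective, so centres could still retrieve the month from their records. And a window that starts at first restrictions would still mix peak and off-peak months, so it reduces the mixing without ending it.

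**Conclusion.** The point holds as a limitation of the planned dataset with a conditional consequence. Every 2020 admission is labelled pandemic care, and nothing on the CRF allows that label to be refined or tested. If early-2020 care and outcomes resembled 2019, the period contrasts are attenuated by the share of unaffected admissions: about 8%, 17% or 25% of the difference for 1, 2 or 3 months (1/12, 2/12, 3/12). For the illustrative 8.7-point mortality difference, that is a loss of 0.7, 1.5 or 2.2 points before rounding of the differences shown.

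The size rests on an assumed number of months, even admissions, a 10% reference rate and a back-solved 18.7%. The attenuation is the lasting argument; the power figures only illustrate it. The primary objective, which guideline items correlate with poor outcomes when disregarded, does not depend on the period boundary. The change is worth making because it is cheap and makes an otherwise untestable assumption testable.

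**What to change.** Add month of admission to CRF Section 2. The identifiers that the Data collection section says will not be recorded do not name it, although that list is open-ended. Keep the calendar-year comparison as planned. Pre-specify a sensitivity comparison limited to admissions after a start date fixed for each country before analysis (for example, first national restrictions), with the same calendar months of 2019 as reference.

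The cost is one extra field, an agreed and dated list of country start dates, one further analysis, and fewer patients in that analysis (150 instead of 200 per group if three months are dropped). The field is best added before or during the planned data-entry window of 1 March to 31 August 2021. Later, centres would have to return to their records.

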#### Data collection (see also the "Analyzed Data" - CRF - paragraph below)

All epidemiological, clinical and surgical data will be collected on a CFR that will be completed by accessing to a protected data system. The link for accessing the completion of the CFR will be sent via email to only one contact person (Local Lead) of each participating center.

#### Sample size

Studies on biliary AP found a mortality rate of approximately 10%. Patients with biliary AP tend to have a higher mortality than patients with alcoholic pancreatitis. However, this rate has been falling over the last 2 decades as improvements in supportive care have been initiated. In patients with severe disease (organ failure), who account for about 20% of presentations, mortality is approximately 30%. This rate has not decreased in the past 10 years.

We estimate that a minimum of 200 patients per group (2019 vs. 2020) would yield a power of 0.80 (1β) to establish whether changes in clinical care for patients with biliary AP during the Covid-19 pandemic has impacted on overall mortality using a one-sided significance a level of 0.05 (5%) with power sample size calculator (sealedenvelope.com).

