#### Background

Acute pancreatitis (AP) is an inflammatory disease of the pancreas, most commonly caused by gallstones or excessive alcohol use. It represents a management challenge and a significant healthcare burden. The incidence of AP ranges globally from 5 to 30 cases per 100.000 inhabitants/year, and there is evidence that the incidence has been rising in recent years. The overall case-fatality rate for AP is roughly 5%, and it is expectedly higher for more severe stages of the disease [1, 2]. In most cases (80%), the outcome of AP is rapidly favorable [3]. However, acute necrotizing pancreatitis (ANP) may develop in up to 20% of cases and is associated with significant rates of early organ failure (38%), needing some surgical/endoscopic intervention (38%), and death (15%) [4].

In the United States, AP is a leading cause of inpatient care among gastrointestinal conditions: more than 270.000 patients are hospitalized for AP annually, at an aggregate cost of over 2.5 billion dollars per year [5]. In Europe, the UK incidence of AP is estimated as 15-42 cases per 100.000/year and is rising by 2.7% each year [6].

Several scientific societies published their clinical practice guidelines making recommendations on the management of AP [7] (Table\_1-4). These guidelines' main topics are the diagnosis, antibiotic treatment, management in the intensive care unit, surgical and operative management, and open abdomen management.

Audits about biliary AP have been performed in Italy, Germany, France, and England, with quite disappointing results [8-11]. Indeed, in these audits, the treatment of biliary AP differed substantially from the recommendations. For example, less than 15% of the responders stated that they strictly followed all recommendations included in the guidelines in Germany, and 25.8% of patients did not receive definitive treatment for biliary AP within one year in the UK [12].

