#### Aim of the study

Since the clinical compliance with recommendations about AP is poor and the impact of implementing guideline recommendations in biliary AP has not been well studied globally, we launched the MANCTRA-1 study intending to demonstrate areas where there is currently a sub-optimal implementation of current guidelines on biliary AP.

Moreover, we argue that during the Covid-19 pandemic, the tendency to disregard the guidelines recommendations has been more marked than usual, and we will try to find out if AP patients' care during the Covid-19 pandemic resulted in a higher rate of adverse outcomes compared to non-pandemic times due to the lack in the compliance of the guidelines.

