#### Statistical analysis

The dichotomous variables will be expressed as numbers and percentages, while continuous variables will be expressed as mean and SD, or median and IQR (minimum and maximum values). Student's t test or ANOVA will be used for comparisons of continuous variables between groups. Chi-squared test or Fisher's exact test, as appropriate, will be used for analysis of categorical data. Multilogistic

regression models will be used to investigate clinical attitudes, physical, laboratory, and radiologic variables predictive of morbidity and mortality. A value of P < 0.05 will be considered statistically significant.

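### The 80% power is stated for a one-sided 5% level, but the analysis section plans a chi-squared test at P < 0.05 with no one-sided rule; run two-sided, 200 per group gives about 70% for the same effect

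*Combined protocol and SAP*

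**What the plan says.** Sample size section: "We estimate that a minimum of 200 patients per group (2019 vs. 2020) would yield a power of 0.80". The level attached to that power is one-sided 5%, and the question is whether changed care "has impacted on overall mortality using a one-sided significance a level of 0.05 (5"%). The section offers one figure that could serve as a baseline, "Studies on biliary AP found a mortality rate of approximately 10"%, but does not say it was the 2019 rate used. It gives neither a 2020 rate nor a difference.

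Statistical analysis section: for binary outcomes, a chi-squared test or Fisher's "exact test, as appropriate, will be used for analysis of categorical data". One threshold covers everything: "A value of P < 0.05 will be considered statistically significant". Sidedness and direction are not mentioned there or anywhere else in the analysis text.

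On direction, the Aim of the study section asks whether care during the pandemic "resulted in a higher rate of adverse outcomes compared to non-pandemic times". The Sample size section asks only about an impact, which could go either way.

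**The concern.** The stated power and the planned test do not visibly belong together. A chi-squared test of a two-by-two table is non-directional unless the plan says otherwise, so an analyst following the Statistical analysis section would normally report a two-sided P value. The 0.80 does not describe that test at the stated minimum. If a one-sided test is meant, the analysis section should name it and give its direction. In a retrospective study that choice would otherwise remain open after the data are seen.

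What is at stake is limited. Mortality by year is listed under Primary outcomes and is the only outcome given a power statement, so a reader would take the 0.80 at face value.

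**Working it through.** **Inputs from the plan.** 200 per group, power 0.80 and one-sided 0.05 (Sample size); chi-squared or Fisher at P < 0.05 (Statistical analysis). Normal quantiles: 1.645 (one-sided 5%), 1.960 (two-sided 5%), 0.842 (80% power).

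**1. The plan's own figure.** It cannot be reproduced, because the 2020 rate is missing. What follows either needs no effect size or rests on a labelled assumption.

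**2. Cost of the change in sidedness, for any effect.** Power of 0.80 one-sided means that the effect divided by its standard error is 1.645 + 0.842 = 2.487. For the same effect and n, two-sided power is Φ(2.487 − 1.960) = Φ(0.527) = 0.70.

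**3. Exact check for a rise in mortality.** The 2019 rates are assumptions. Two have a loose anchor in the documents: 10% in the Sample size section, and 5% in the Background section ("The overall case-fatality rate for AP is roughly 5"%, for all acute pancreatitis). The 2020 rate is the one giving 80% one-sided by the unpooled normal formula. Power is then found by enumerating both binomials with 200 per group, using the two-sided chi-squared test without continuity correction.

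| 2019 rate | 2020 rate | Two-sided power | Smallest expected cell count, 200 × mean rate |
|---|---|---|---|
| 3% | 8.8% | 0.71 | 12 |
| 5% | 11.9% | 0.70 | 17 |
| 10% | 18.6% | 0.70 | 29 |
| 15% | 24.9% | 0.70 | 40 |

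**4. Where the figure moves.** For a fall from 5% to about 0.85%, exact two-sided power is about 73%. If the 200 came from a continuity-corrected one-sided formula (10% versus about 19.3%), two-sided power is about 76%.

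**5. Number that restores 0.80 two-sided.** The ratio is ((1.960 + 0.842) / (1.645 + 0.842))² = (2.802 / 2.487)² = 1.27, and 1.27 × 200 is about 254 per group. Exact power at 254 per group for 10% versus 18.64% is 0.80.

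**6. Another possible origin of the 200.** Assume 10% versus 20%, two-sided 5%, 80% power. The unpooled formula gives (0.10 × 0.90 + 0.20 × 0.80) × 2.802² / 0.10² = 0.25 × 7.85 / 0.01, or about 196 per group. The pooled formula gives 199. Exact chi-squared power at 200 per group is 0.81. So 200 fits a two-sided calculation with round inputs as well.

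**7. Fisher, as a side note.** For the rises in step 3, two-sided Fisher has about 64 to 65% power. Part of that loss is the test's own conservatism: one-sided Fisher at 10% versus 18.7% already has only about 76%. With smallest expected counts of 12 to 40, chi-squared is the test likely to apply, so 70% is the figure to use.

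**The case against.** The strongest reply is that nothing in the plan contradicts anything else. A one-sided mortality test at P < 0.05 satisfies both sections, the aim supplies a direction, and the 0.80 would then stand for the unstated effect. The two-sided reading rests on convention. This is right as far as it goes: a reader might infer that the protocol prescribes a two-sided test, or that the sample size contains an arithmetic error, and the documents support neither. What remains is that no section specifies a one-sided analysis, and the sample size wording is non-directional. The power is therefore tied to a test that the analysis section does not describe.

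A second reply is that the 200 may never have come from a one-sided calculation. Step 6 shows that this is possible. It is equally unproven, because the inputs are not given. In that case there is no shortfall, and the word one-sided is what needs correcting.

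A third reply is that little depends on the 0.80. The study is retrospective, 200 is a minimum, and the population is "All consecutive adult patients admitted to the participating surgical departments" and meeting the diagnosis over two years, with no cap. The stated primary objective is about disregarded guideline items, and the comparisons between years appear under Secondary objectives. All of this stands and is why the point is minor. A reader might infer that the study is underpowered or must recruit more. The documents do not support that, since they give no expected accrual.

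**Conclusion.** The concern holds as an inconsistency between the stated power and the planned test. If mortality is tested with the usual two-sided chi-squared test, power at 200 per group is about 70% for the effect that gives 80% one-sided. Exact values are 70 to 71% for rises from 3 to 15%, with the exceptions in step 4 of about 73% and 76%. This rests on taking the word one-sided as the true input. If it is a slip and the inputs resembled 10% versus 20% two-sided, power is about 81%. Only the sponsor can say which. A headline figure of 65% would be too strong, because it depends on Fisher's test, which the expected counts make unlikely. Severity: minor.

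**What to change.** No change to enrolment or data collection.

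1. In Sample size, state the 2019 and 2020 mortality rates actually entered in the calculator. They should come from the record of the calculation, not be worked back from 200.
2. Make the sidedness the same in Sample size and Statistical analysis.
   - If testing is two-sided, say so in both places and restate the power at 200 per group for the two-sided chi-squared test. If the original inputs were two-sided, deleting the word one-sided and giving the rates is enough.
   - If one-sided testing is intended, write the one-sided mortality test and its direction into Statistical analysis.

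The cost is a few sentences in two paragraphs. The downside is that the stated power at the minimum may look less favourable. Actual power will be higher if accrual exceeds 200 per group.
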